6.9 Safety analyses

All safety summary tables, figures, and listings will be based on the SAF unless otherwise specified.

6.9.1 Extent of exposure

6.9.1.1 Exposure

Exposure is a priori defined as the difference between the number of tablets dispensed and the number of tablets returned or lost. However, for a substantial number of subjects the information

about tablets lost is missing and is therefore assumed to be 0. To account for this, exposure will be calculated as the minimum of the difference between the number of tablets dispensed and the number of tablets returned or lost, and the treatment duration.

The number of tablets taken will be summarised by treatment group.

6.9.1.2 Treatment duration

The duration of treatment for each subject will be calculated from the date of first dose up until (and including) the date of last IMP administration.

Treatment duration (days) will be summarised by treatment group.

6.9.1.3 IMP compliance

IMP compliance (%) will be calculated for each subject as number of tablets taken divided by the treatment duration (days) multiplied by 100.

IMP compliance (%) will be summarised by treatment group.

Percentage IMP compliance will be summarised by treatment group.

6.9.1.4 eDiary compliance

eDiary compliance (%) for the TPS will be calculated as the number of non-missing eDiary entries in the TPS divided by total number of days in the TPS.

eDiary compliance (%) will be summarised by treatment group.

6.9.2 Adverse events

MedDRA version 23.1 will be used for reporting of AEs.

6.9.2.1 Events of special interest

Events of special interest for this trial are:

- Systemic allergic reactions including anaphylaxis
- Events treated with adrenaline/epinephrine
- Severe local swelling or oedema of the mouth and/or throat
- Oral allergy syndrome
- Eosinophilic oesophagitis
- Asthma exacerbations

6.9.2.2 Reporting of adverse events

AE is considered a TEAE if the time of onset is after the time of first dose of IMP and at most 7 days after last dose of IMP.

All TEAEs will be summarised by treatment group according to causality, severity (mild, moderate, severe), seriousness, action taken, outcome, and whether the event led to IMP discontinuation. The number of subjects in each treatment group, the number and frequency of

subjects having the event, as well as the number of events and proportion of events will be displayed. A similar summary table will be produced for all IMP-related TEAEs.

All TEAEs and all IMP-related TEAEs will be summarised (in separate tables) by treatment group, SOC, and PT, displaying number of subjects in treatment group, and number and frequency of subjects having the event. The tables will be sorted according to most frequent SOC and PT in the active treatment group, and the most common TEAEs (preferred term from MedDRA) defined as those that are present in at least 5% of subjects in the active treatment group will be marked.

Severe TEAEs will be listed only, if there are fewer than 10 events in total. Otherwise, severe TEAEs will also be summarised similar to how TEAEs are presented. The same applies for SAEs, IMP-related SAEs, TEAEs leading to IMP interruption, and TEAEs leading to IMP discontinuation.

For most frequent IMP-related TEAEs (present in at least 5% of subject in the active treatment group) onset and duration will be presented as follows: Average time to onset and average duration both in days, will be presented by PT and treatment. In addition, for day 1 of treatment average time to onset in day and minutes will be presented by SOC, PT, and treatment.

For the most frequent IMP-related TEAEs which are recurrent, the average daily duration and the average duration in days from first to last occurrence will be presented by SOC, PT and treatment.

Most frequent non-serious TEAEs in any arm (≥ 1 and $\geq 5\%$) will be summarised by system organ class and preferred term.

A table with the overall summary of the safety profile will be produced showing subjects with TEAEs, IMP-related TEAEs, IMP-related severe TEAEs, IMP-related treatment-emergent SAEs, IMP-related TEAEs leading to IMP discontinuation, and each type of IMP-related treatment-emergent ESI by treatment group.

Serious TEAEs, severe TEAEs, TEAEs leading to discontinuation, individual ESIs, and all non-treatment emergent adverse events will be listed.

The 6 different types of ESIs will be summarised by SOC, PT, and treatment group.

Medication errors, including overdose, abuse and misuse of the IMP will be listed.

In addition to above a plot of the most frequent ($\geq 5\%$, in active arm) IMP-related TEAS by SOC and PT will be produced. Furthermore, plots of the median duration in days and time to onset in days of most frequently ($\geq 5\%$) reported IMP-related AEs of subjects in active treatment group.

6.9.2.3 Local administration site TEAEs

The AEs identified as local administration site TEAEs, by comparison against a pre-defined list of MedDRA PTs, will be summarised separately. The pre-defined list of PTs is given in section Appendix A.

IMP-related local administration site reactions TEAEs will be summarised similar to all TEAEs by treatment group according to causality, severity (mild, moderate, severe), seriousness, action taken, outcome, and whether the event led to IMP discontinuation.

6.9.3 Additional safety assessments

Shift tables will be produced for physical examination, and laboratory assessments (chemistry, haematology, and urinalysis) for baseline to EOT.

In addition to above laboratory assessments (chemistry and haematology), vital signs and the pulmonary function test parameters (FVC, FVC percent predicted, FEV₁, and FEV₁ percent predicted) will be summarised by visit and treatment group.

Results from the pregnancy test for female subjects of child-bearing potential will be listed.

6.10 Interim analysis

No interim analysis was planned.

6.11 Changes and/or deviations to protocol-planned analyses

In addition to the analyses specified in the CTP a supplementary analysis for the primary endpoint has been added where subjects with potential data issues will be excluded from the main analysis.

The secondary endpoints (average TCS during the AHPS and OPS, average DSS during the AHPS and OPS, average DMS during the AHPS and OPS, and average TCS (EAACI scoring) during BPS and TPS) will be analysed by using the hypothetical estimand and main estimator only.

Local administration site reactions are specified as 'treatment-related local administration site TEAEs.

The reasons for IMP discontinuation will be visualised by a band plot, instead of a Kaplan-Meier plot as the band plot also shows the different reasons for discontinuation.

Physical examination will not be summarized by visit as stated in the CTP, instead a shift table will be made from baseline to end of treatment. 5-, 25-, 75-, and 95 percentiles will not be presented for tabulation of data by visit as stated in the CTP.

The exploratory assessment of the levels of serum antibodies/serum components/serum markers to relevant allergens will not be performed nor reported in a separate document as stated in CTP.

Due to the amount of missing pollen data, it was deemed necessary to perform a visual inspection of all species by pollen station instead of the pollen plots (pollen grains/m³ versus time) as the approach chosen is more precise.

7 Sample size determination

Sample size calculations are based on the primary endpoint, the average TCS during the BPS, which will be square root transformed prior to analysis in order to better approximate the normal distribution. Based on previous ALK SLIT-tablet studies in both adult and paediatric populations, it is assumed that the mean of the square root transformed average TCS during the BPS in the placebo group is 2.5 with corresponding common standard deviation of 1.4 in both placebo and active groups.

Analyses for the primary and secondary estimands will include all randomised subjects and use different multiple imputation strategies to account for missing data. For the purposes of sample size estimation, it is assumed that 5% of observations in the active arm are imputed from the placebo arm. A true relative treatment effect of 25% is assumed, which corresponds to an effective relative treatment effect of 23.75% after placebo imputation.

For a range of sample sizes and a 1:1 randomisation ratio between active and placebo groups, 1000 trial datasets were simulated under the above assumptions and each trial was analysed using a linear model with a fixed term for treatment. For each choice of sample size, the probability of the trial fulfilling the regulatory requirements of both the EMA and FDA for the primary endpoint was assessed over all the simulated trials.

The following regulatory requirements were considered:

1. Statistical significance of the absolute treatment effect (EMA)
2. Point estimate of the absolute treatment effect greater than 1 (EMA)
3. Point estimate of the relative treatment effect greater than 15% (FDA)
4. Lower limit of the 95% CI for the relative treatment effect greater than 10% (FDA)

Based on the results of the simulation trial, 500 randomised subjects per arm (1000 subjects in total) was chosen to provide at least 85% power to satisfy regulatory requirements 1, 2 and 3 for the analyses based on all randomised subjects (assuming 5% imputation of placebo in the active arm for missing data). Assuming 10% of the 1000 randomised subjects do not have any diary data during the BPS, the power for an observed case (OC) analysis to meet the requirements is also presented.

Table 7: Power to meet regulatory criteria for FAS and Observed Case Analyses

	Statistical significance of absolute treatment effect	Point estimate of absolute treatment effect >1	Point estimate of relative treatment effect >15%	Lower limit of 95% CI for relative treatment effect >10%
FAS analysis ^{1,3} n=500 ² per arm	95.0%	88.3%	92.8%	60.2%
OC analysis ^{1,4} n=450 ² per arm ³	94.7%	89.9%	93.9%	62.2%

¹FAS analysis includes all randomised subjects, OC analysis includes all randomised subjects with diary data in the BPS

²n=number of subjects included in the analysis

³Assumptions: placebo mean=2.5, SD=1.4 (active & placebo), true relative treatment effect=25%, 5% of active arm imputed from placebo

⁴Assumptions: placebo mean=2.5, SD=1.4 (active and placebo), true relative treatment effect=25%, no MI, 10% of 1000 randomised subjects excluded due to missing data

8 Demographics and baseline characteristics

8.1 Screening failures

A summary of reasons for screening failure will be presented for the total analysis set.

8.2 Protocol deviations

Overall important PDs will be summarised by trial-, country-, site- and subject-level. Furthermore, the important PDs will be summarized by the subject-level deviations and treatment.

A listing with all important PDs will be presented. In addition, a listing with subjects who had TC4 before V6 will be presented.

8.3 Subject disposition

Subject disposition will be summarised by number and percentage of subjects screened, randomised, included in the analysis sets, completed trial, discontinued trial, reason of discontinuation of trial, completed IMP, discontinued IMP, and reason for IMP discontinuation by treatment group.

IMP discontinuations over time by different reasons will be visualised by a band plot showing proportions on treatment, having discontinued treatment due to AE, withdrawal by subject, and all other reasons (pooled).

Screening failures will be summarised by reason.

8.4 Baseline characteristics

Demographic variables (age, age group, sex, race, ethnic origin, and country) will be summarised by treatment group.

Baseline characteristics (mono/poly sensitised, duration of AR/C induced by birch pollen, skin prick test results, skin prick test wheal sizes (birch), specific IgE to birch, and asthma status) will be summarised by treatment group.

8.5 Medical history

Medical history is coded using the MedDRA version 23.1 and will be summarised by treatment group.

Separate tables will be created for allergy or asthma history and other medical history. In addition, the other medical history will also be summarised by PT and SOC.

8.6 Prior and concomitant therapy

Prior and concomitant medication will be coded according to the WHO drug dictionary and summarised separately by treatment group.

9 Supporting documentation

9.1 Definition of pollen seasons

Each site was allocated to a pollen region prior to unblinding.

The different pollen seasons varied across the selected pollen regions both in intensity and duration.

BPS

For each pollen region and year the BPS were defined as follows:

Start date: The start date of the BPS is defined as the first day of 3 consecutive days with pollen count larger than or equal to 30 grains/m³

Stop date: The stop date of the BPS is defined as the last day in the last occurrence of 3 consecutive days with pollen count larger than or equal to 30 grains/m³

Alder, Hazel and Oak

The alder, hazel, oak pollen seasons were defined as the days included in any of the alder, hazel, and oak pollen seasons:

Start date: The start date of the pollen season is defined as the first day of 3 consecutive days with pollen count larger than or equal to 10 grains/m³

Stop date: The stop date of the pollen season is defined as the last day in the last occurrence of 3 consecutive days with pollen count larger than or equal to 10 grains/m³

Based on experience from trial TT-04, it is anticipated that there will be a high degree of overlap between the alder and hazel seasons. As such, a combined alder-hazel season is defined for each pollen station as follows:

[figure not shown]
Start date: The start date of the alder-hazel pollen season is the earliest of the alder season start date and hazel season start date

Stop date: The stop date of the alder-hazel pollen season is the latest of the alder season stop date and the hazel season stop date

TPS

The TPS is defined as all days included in any of the alder, birch, hazel, oak pollen seasons. The TPS is not necessarily a continuous period, an example is illustrated in Figure 3.

Figure 3: Example of tree pollen season with non-continuous period

In case of missing pollen counts for specific pollen stations one of the 3 approaches was applied prior to unblinding:

- For pollen stations with missing data between observed start and stop date of the season LOCF was applied.
- For pollen stations with either very sparse data or completely missing data, each station was assigned a neighboring station as close as possible to the original station where data was available. Pollen counts from the backup station was used and in addition a sanity check was made by looking into the historical pollen data for the original pollen station.

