15.10.2 Alder, hazel and oak pollen season definition

For each pollen region, the hazel, alder and oak pollen seasons is defined in each year as follows:

- Start date: The start date of the pollen season is defined as the first day of 3 consecutive days with pollen count larger than or equal to 10 grains/m³
- Stop date: The stop date of the pollen season is defined as the last day in the last occurrence of 3 consecutive days with pollen count larger than or equal to 10 grains/m³

Clinical trial protocol	Date:	24-May-2020	
Trial ID: TT-06	Version:	3.0	
EudraCT No: 2020-004372-17	Status:	Final	
CONFIDENTIAL	Page:	83 of 99	

Based on experience from trial TT-04, it is anticipated that there will be a high degree of overlap between the alder and hazel seasons. As such, a combined alder-hazel season is defined for each pollen region as follows:

- Start date: The start date of the alder-hazel pollen season is the earliest of the alder season start date and hazel season start date
- Stop date: The stop date of the alder-hazel pollen season is the latest of the alder season stop date and the hazel season stop date

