9.2.2.3 Average Daily Rhinoconjunctivitis Total Combined score (average TCS)

The average TCS during a given pollen season is the mean of all non-missing daily TCS over all days in the selected pollen season. Average TCS will be derived for the BPS, TPS, AHPS, OPS [REDACTED] The definitions of the pollen seasons are provided in section 9.1.

[REDACTED]
[REDACTED]
[REDACTED]
[REDACTED]

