Appendix D Final pollen season

pollen_station	Season	Cohort	Start_date	End_date	Average grains/m3	Neighbouring	comments
ATWIEN	ALDER	1	05-02-2022	30-03-2022	95,6		
CZTRIN	ALDER	1	13-02-2022	30-03-2022	110,1		
DEAACH	ALDER	1	09-02-2022	08-03-2022	47		
DEBOCH	ALDER	1	07-02-2022	13-03-2022	54,7		
DEBORS	ALDER	1	27-01-2022	25-03-2022	109,8		
DEDRES	ALDER	1	12-02-2022	24-03-2022	55		
DELEVE	ALDER	1	07-02-2022	13-03-2022	27,2		
DELOEW	ALDER	1	04-02-2022	22-03-2022	52,8		
DEMARB	ALDER	1	08-02-2022	23-03-2022	64,7		
DEMOEN	ALDER	1	07-02-2022	13-03-2022	34,7		
DKCOPE	ALDER	1	12-02-2022	15-03-2022	20		
FRSTRA	ALDER	1	02-02-2022	28-03-2022	324,8		
HUGYOE	ALDER	1	03-02-2022	26-03-2022	84,7		
HUMISK	ALDER	1	05-02-2022	01-05-2022	36,3		
HUPEST	ALDER	1	04-02-2022	30-03-2022	118,2		
HUSALG	ALDER	1	05-02-2022	03-04-2022	107,4		
HUSZE2	ALDER	1	15-02-2022	29-03-2022	65,2		
LTSIAU	ALDER	1	24-02-2022	28-03-2022	82,3		
LTVILN	ALDER	1	25-02-2022	05-04-2022	63,5		
PLBYDG	ALDER	1	13-02-2022	06-04-2022	171,7		
PLCRAC	ALDER	1	13-02-2022	28-03-2022	156,3		
PLKATO	ALDER	1	08-02-2022	04-04-2022	126,5		
PLLODZ	ALDER	1	13-02-2022	02-04-2022	180,8		
PLLUBL	ALDER	1	15-02-2022	29-03-2022	120,6		
PLPTRY	ALDER	1	08-02-2022	05-04-2022	175,1		
PLSZCZ	ALDER	1	05-02-2022	14-03-2022	51,5		
RUMOSC	ALDER	1	14-03-2022	12-04-2022			
SKBRAT	ALDER	1	09-02-2022	09-04-2022	113,6		
ATWIEN	ALDER	2	20-02-2023	11-03-2023	19,3		
BEBRUS	ALDER	2	08-02-2023	23-03-2023	133,4	NLLEID	completely missing
BEMARC	ALDER	2	07-02-2023	24-03-2023	153,8	DEMOEN	completely missing
CZTRIN	ALDER	2	07-03-2023	10-03-2023	27,5		
DEBOCH	ALDER	2	13-02-2023	22-03-2023	141,2		
DEDRES	ALDER	2	16-02-2023	03-03-2023	71,8		
DELEVE	ALDER	2	07-02-2023	24-03-2023	153,8	DEMOEN	partially missing
DELIPP	ALDER	2	16-02-2023	21-03-2023	83,1		

DELOEW	ALDER	2	15-02-2023	06-03-2023	76,5		
DEMARB	ALDER	2	22-02-2023	18-03-2023	63,4		
DEMOEN	ALDER	2	07-02-2023	24-03-2023	153,8		
DEMUNC	ALDER	2	16-02-2023	10-03-2023	38		
DKCOPE	ALDER	2	11-02-2023	03-04-2023	41,8		
DKVIBO	ALDER	2	01-03-2023	03-04-2023	12,8		
FRSTRA	ALDER	2	02-02-2023	14-03-2023	127,7		
HUGYOE	ALDER	2	17-02-2023	10-03-2023	45,3		
HUMISK	ALDER	2	21-02-2023	05-03-2023	18,9		
HUPEST	ALDER	2	17-02-2023	10-03-2023	25,3		
HUSALG	ALDER	2	18-02-2023	17-03-2023	25,3		
HUSZE2	ALDER	2	17-02-2023	02-03-2023	35,6		
LTSIAU	ALDER	2	19-03-2023	11-04-2023	46		
LTVILN	ALDER	2	14-03-2023	25-03-2023	138,5		
MONTREAL	ALDER	2	09-04-2023	11-05-2023	35,8		
NLLEID	ALDER	2	08-02-2023	23-03-2023	133,4		

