BEMARC	HAZEL	2	31-12-2022	12-04-2023	28,9	DEMOEN	completely missing
CZTRIN	HAZEL	2	11-01-2023	26-02-2023	29,5		
DEBOCH	HAZEL	2	05-01-2023	23-02-2023	58,1		
DEDRES	HAZEL	2	03-02-2023	02-03-2023	37,3		
DELEVE	HAZEL	2	05-01-2023	07-01-2023	29,3		
DELIPP	HAZEL	2	13-02-2023	27-02-2023	39,9		
DELOEW	HAZEL	2	15-02-2023	06-03-2023	42,7		
DEMARB	HAZEL	2	05-01-2023	12-03-2023	10,3		
DEMOEN	HAZEL	2	31-12-2022	12-04-2023	28,9		
DEMUNC	HAZEL	2	04-01-2023	10-03-2023	31,7		
DKCOPE	HAZEL	2	11-02-2023	21-02-2023	25,1		
FRSTRA	HAZEL	2	02-01-2023	10-03-2023	89,6		
HUGYOE	HAZEL	2	13-01-2023	21-02-2023	5,8		
HUMISK	HAZEL	2	17-02-2023	13-03-2023	29,3		LOCF
HUPEST	HAZEL	2	01-01-2023	16-03-2023	17,4		
HUSALG	HAZEL	2	27-01-2023	16-03-2023	22,1		
HUSZE2	HAZEL	2	07-01-2023	10-03-2023	14,5		
LTSIAU	HAZEL	2	19-03-2023	22-03-2023	43,7		
LTVILN	HAZEL	2	18-03-2023	24-03-2023	51,4		
NLLEID	HAZEL	2	06-01-2023	18-02-2023	6		
PLBYDG	HAZEL	2	10-01-2023	19-03-2023	14		
PLCRAC	HAZEL	2	10-01-2023	14-03-2023	11,3		
PLKATO	HAZEL	2	21-02-2023	19-03-2023	18,7		
PLLODZ	HAZEL	2	17-03-2023	19-03-2023	14,7		
PLLUBL	HAZEL	2	06-02-2023	15-03-2023	15,6	PLPTRY	completely missing

PLPTRY	HAZEL	2	06-02-2023	15-03-2023	15,6		
PLSZCZ	HAZEL	2	10-01-2023	19-03-2023	14	PLBYDG	completely missing
SKBRAT	HAZEL	2	17-02-2023	11-03-2023	25,6		
SKNITR	HAZEL	2	17-02-2023	11-03-2023	25,6	SKBRAT	completely missing
ATWIEN	OAK	1	24-04-2022	20-05-2022	134,2		
CZTRIN	OAK	1	02-05-2022	22-05-2022	84,9		
DEAACAH	OAK	1	14-04-2022	17-05-2022	253,3	DEMOEN	completely missing
DEBOCH	OAK	1	18-04-2022	14-05-2022	353,4		
DEBORS	OAK	1	01-05-2022	22-05-2022	786,7		
DEDRES	OAK	1	28-04-2022	11-05-2022	582,1		
DELEVE	OAK	1	14-04-2022	11-05-2022	193		
DELOEW	OAK	1	14-04-2022	13-05-2022	89,7		
DEMARB	OAK	1	03-05-2022	20-05-2022	430,1		
DEMOEN	OAK	1	14-04-2022	17-05-2022	253,3		
DKCOPE	OAK	1	11-05-2022	22-05-2022	60,5		
FRSTRA	OAK	1	13-04-2022	20-05-2022	136		
HUGYOE	OAK	1	30-04-2022	12-05-2022	32,2		
HUMISK	OAK	1	29-04-2022	22-05-2022	65,3		
HUPEST	OAK	1	24-04-2022	22-05-2022	91,3		
HUSALG	OAK	1	24-04-2022	23-05-2022	196,2		
HUSZE2	OAK	1	14-04-2022	19-05-2022	42,9		
LTSIAU	OAK	1	17-05-2022	28-05-2022	25,1		
LTVILN	OAK	1	19-05-2022	27-05-2022	40,4		
MONTREAL	OAK	1	13-05-2022	19-05-2022	32,6		LOCF
PLBYDG	OAK	1	28-04-2022	24-05-2022	74,9		
PLCRAC	OAK	1	28-04-2022	16-05-2022	101,2		
PLKATO	OAK	1	15-04-2022	21-05-2022	57,9		
PLLODZ	OAK	1	05-05-2022	21-05-2022	124,5		
PLLUBL	OAK	1	05-05-2022	21-05-2022	76,1		
PLPTRY	OAK	1	30-04-2022	23-05-2022	97,3		

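### The alder-hazel season is one unbroken span, so at three stations it counts days that lie in neither season and outside the tree pollen season; the effect on the supportive AHPS averages is small

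*SAP*

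**What the plan says.** SAP 9.1 sets the AHPS by two rules. The start is "The start date of the alder-hazel pollen season is the earliest of the alder season start date and hazel season start date". The end is "The stop date of the alder-hazel pollen season is the latest of the alder season stop date and the hazel season stop date". The result is one continuous block of days. Protocol 15.10.2 has the same rules and gives the reason, drawn from experience in TT-04: "it is anticipated that there will be a high degree of overlap between the alder and hazel seasons". Neither document says what to do where the two seasons do not meet.

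The same section of the SAP builds the TPS differently: "The TPS is defined as all days included in any of the alder, birch, hazel, oak pollen seasons". It adds that the TPS may be broken into separate periods, so days between species seasons drop out.

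The scores are then averaged over whatever days the season contains. SAP 9.2.2.3: "The average TCS during a given pollen season is the mean of all non-missing daily TCS over all days in the selected pollen season". SAP 9.2.2.1 and 9.2.2.2 do the same for the symptom score (DSS) and the medication score (DMS). Average TCS, DSS and DMS in the AHPS are secondary endpoints (protocol 2.10; SAP Table 1). Appendix D of the SAP lists final dates for each single species but has no rows for the combined season.

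**The concern.** A span from earliest start to latest end is harmless while the two seasons overlap or adjoin. Where they do not, every day between them is labelled AHPS although neither species is in season. Two rules in one section then treat the same kind of gap in opposite ways: the TPS leaves it out and the AHPS keeps it in.

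The AHPS averages are meant to describe symptoms and medication use under alder and hazel exposure. A gap day with a diary entry has the same weight as any other day. If scores on such days show little treatment difference, they pull the absolute difference in the AHPS averages towards zero. Because Appendix D shows only single-species dates, a reader would not see this without working it out.

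**Working it through.** The plan states no AHPS length or gap count, so there is no figure of its own to reproduce. The check is date arithmetic on SAP Appendix D, counting both end days. A station-season is one pollen station in one cohort. The station code DEAACAH in the hazel rows was read as DEAACH.

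**Step 1. Base.** Cohort 1 has 28 alder and 27 hazel seasons, with 27 stations having both. Cohort 2 has 36 and 31, with 31 having both. So 27 + 31 = 58 station-seasons have both species. Six more have alder only (DKCOPE in cohort 1; DKVIBO, MONTREAL, PLBIAL, PLWROC and QUEBEC in cohort 2), where no gap can arise.

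**Step 2. Formulas.**
- Span = days from min(alder start, hazel start) to max(alder end, hazel end).
- Union = days in the alder or the hazel season, each counted once.
- Gap = span − union.

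**Step 3. Results.** The gap is zero in 55 of the 58. The other three are:

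| Station, cohort | Hazel (days) | Alder (days) | Span | Union | Gap | Gap dates |
|---|---|---|---|---|---|---|
| DELEVE, 2 | 5 Jan–7 Jan 2023 (3) | 7 Feb–24 Mar 2023 (46) | 79 | 49 | 30 (38.0%) | 8 Jan–6 Feb |
| CZTRIN, 2 | 11 Jan–26 Feb 2023 (47) | 7–10 Mar 2023 (4) | 59 | 51 | 8 (13.6%) | 27 Feb–6 Mar |
| PLSZCZ, 1 | 28–30 Jan 2022 (3) | 5 Feb–14 Mar 2022 (38) | 46 | 41 | 5 (10.9%) | 31 Jan–4 Feb |

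Total gap: 30 + 8 + 5 = 43 days. Total span over the 58: 3,180 days. 43 / 3,180 = 1.4%. Adding the 155 days of the six alder-only station-seasons gives 43 / 3,335 = 1.3%.

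**Step 4. Position relative to the TPS.** Birch and oak begin on 5 April and 25 April 2023 at DELEVE, 13 April and 11 May 2023 at CZTRIN, and 18 April and 7 May 2022 at PLSZCZ. All 43 gap days come earlier, so none is a TPS day.

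**Step 5. Where the largest gap comes from.** The two DELEVE rows read "DELEVE HAZEL 2 05-01-2023 07-01-2023" and "DELEVE ALDER 2 07-02-2023 24-03-2023 153,8 DEMOEN partially missing". The alder dates are those of the neighbouring station DEMOEN, while the hazel dates are DELEVE's own. DEMOEN's hazel season in cohort 2 runs from 31 December 2022 to 12 April 2023 and contains the whole alder season. With those hazel dates DELEVE has no gap, and 43 − 30 = 13 gap days remain, at two stations.

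**Step 6. Size of the dilution.** Let g be the gap share of AHPS days. If diaries are complete and the arms do not differ on gap days, the difference in daily means over the AHPS is (1 − g) times the difference over the union days, so it shrinks by g. With equal weight per station-season, the average shrinkage is (38.0 + 13.6 + 10.9) / 58 = 62.5 / 58 ≈ 1.1%, or 62.5 / 64 ≈ 1.0% with the alder-only station-seasons included. With DEMOEN hazel dates at DELEVE it is (13.6 + 10.9) / 58 ≈ 0.4%. This is arithmetic on the untransformed scale. The model works on square roots, so the figures show the order of magnitude.

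**The case against.** The case for leaving the rule alone has several parts.

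- **It was pre-specified.** The protocol set the span and the SAP repeats it. Each single-species season is also a span that bridges low-count days: hazel in cohort 2 averages 6 grains/m³ at NLLEID and 5.8 at HUGYOE, below the threshold of 10. This stands as a limit on what a union can achieve, since those days would stay in. It does not answer the point that the only reason given for the span, overlap, fails at these three stations.
- **Most gap days come from one mixed record.** Thirty of the 43 arise at DELEVE from pairing two stations' data, and DELEVE's own alder counts were incomplete. This stands.
- **Dilution is inferred.** Only days with a diary entry count. Recording starts at the TC2 call, at the expected start of the TPS (protocol section 10). The expected dates are in protocol Appendix 5, which is not in the text available here. In cohort 1, DELEVE's alder and hazel seasons began on 7 and 12 February 2022. If the expected start for cohort 2 was similar, many January gap days may have no entries. Protocol 3.1 also lets diary dates be updated, so this cannot be settled. It stands.
- **Inference is barely touched.** If gap-day scores are near zero in both arms, both averages scale down together and the relative difference at that station hardly moves. The random effect for station within cohort absorbs much of the level shift. This largely stands.

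A reader might infer three stronger things. One is that DELEVE's AHPS averages are cut by 38%. That figure is a ceiling at one station: it needs complete diaries and near-zero scores on every gap day, and the number of subjects there is not given. Another is that the AHPS contradicts the TPS definition. Both documents build the TPS from the four single-species seasons, and neither says that the combined season must be a subset of it. The third is that gap days are pollen-free. They only lie outside the start and end dates set by the three-day threshold rule.

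**Conclusion.** The point holds, and it is minor. On the plan's own dates the span rule counts 43 days, 1.4% of AHPS days where both species have a season, that belong to neither season and not to the TPS. That part is exact. The dilution is the expected direction but is not shown. Its extent depends on diary entries on those days and on subjects per station, neither of which is given. With complete diaries, no treatment difference on gap days and equal weight per station-season, the absolute difference shrinks by about 1% on average.

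The AHPS averages are outside the nine-step testing hierarchy, and SAP 4.1.1 treats such endpoints as supportive. The primary endpoint (birch season), the key secondary endpoints (birch season and TPS) and the control of type I error are unaffected.

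**What to change.** In SAP 9.1, define the AHPS as all days in the alder season or the hazel season, allowing breaks, in the same way as the TPS, and derive the AHPS averages on those days. Three station-seasons change: DELEVE cohort 2 from 79 to 49 days, CZTRIN cohort 2 from 59 to 51, and PLSZCZ cohort 1 from 46 to 41. Record the change from protocol 15.10.2 in SAP 6.11.

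The cost is one sentence in SAP 9.1, an entry in 6.11 and a small change to the season derivation, with no new data. The downside is a recorded departure from the protocol's definition, made after the season dates were fixed, although those dates do not depend on treatment.

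If the data are already unblinded, keep the span as the planned analysis and report a union-based sensitivity analysis, labelled as such, in the trial report.
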